11.1. STUDY HYPOTHESES

How are endogenous µ-opioid mechanisms affected in migraine patients?

Aim 1. To demonstrate that clinical and experimental pain measures in migraine patients are associated with μ OR BP_{ND} in the thalamus and other pain-related regions, even during interictal phase (non-headache phase).

We hypothesize that migraine patients will have a reduction in μ OR BP_{ND} at the baseline level. The activation of μ OR neurotransmission, calculated as reduction in μ OR BP_{ND} during a sustained thermal pain threshold stress challenge, will also be lower than in controls and both these measures will be associated with clinical and experimental pain ratings.

Feasibility: (Aim1) During the K23 NIH-NINDS award period, we evaluated *in vivo* the μ -opioid system during spontaneous episodic migraine headaches. Seven patients were scanned at interictal and ictal phases using the selective μ -opioid receptor (μ OR) radiotracer [¹¹C]carfentanil (Figure 11). In the ictal phase there was dysfunctional μ OR activation in the medial prefrontal cortex (mPFC), an area highly related to clinical pain processing. Furthermore, μ -opioid binding changes in mPFC showed moderate negative correlation with the combined extension and severity of the attacks. These results indicated for the first time the acute activation of the endogenous μ -opioid neurotransmission interacting with μ OR due to the pain of the migraine attack (DaSilva et al., 2014a).

(Aim 1.2) When challenged for sustained thermal stimulus on the trigeminal ophthalmic region (STPTS) during the ictal and interictal phases, six of those migraineurs showed ictal allodynia that was concurrent and positively correlated with μ OR activation in the midbrain, extending from red nucleus to vIPAG. These findings demonstrate for the first time *in vivo* the high μ OR activation in the migraineurs' brains in response to their allodynic experience (Figure 12 & 13)(Nascimento et al., 2014b).

We then compared the migraineurs in the interictal phase with age and gender matched healthy controls. In our preliminary data we noticed lower μ OR BP_{ND} in pain-related brain regions, especially the thalamus (Figure 14), at baseline (no stimulus) (Aim1.1) and during thermal stimulation (STPTS) (Aim1.2). These results indicate that there is higher endogenous μ -opioid neurotransmission interacting with μ OR in migraineurs, even during the interictal phase, either by the higher occupancy or loss of μ -opioid receptors available.

Analysis: First, we will continue to examine differences in baseline µOR BP_{ND} and in the activation of µ-opioid neurotransmission in a large control sample of migraine patients to confirm our preliminary results. A mixed model of variance will be employed, accounting for age and other nuisance or potentially influencing variables (e.g., plasma levels of estradiol, proximity of attacks). Reductions in baseline µOR BP_{ND} and in the activation of u-opioid neurotransmission in migraine compared to controls should be expected. Second, we will investigate individual associations between baseline uOR BP_{ND} levels and their change during the STPTS challenge in the thalamus, other pain-related regions, and acute and chronic pain measures, as well as between µOR BP_{ND} levels and pain frequency by means of pair-wise correlation coefficients. We intend to use either Pearson's version or the Spearman's rank version of the correlation coefficient depending on whether the variables investigated follow normal distribution or not. Subsequently, we shall investigate the joint effect of pain intensity and frequency on the μORBP_{ND} by means of a multiple linear regression analysis where μOR BP_{ND} is the outcome, and the other two are used as predictor clinical variables. The linear regression analysis allows us to identify the effect of either one on µOR BP_{ND} for a fixed level of the other predictor.

Potential pitfalls and alternative strategy: Regarding possible negative results we have to explore other scenarios: First, our hypothesis was wrong. However, this is unlikely due to extensive data from our group showing decreased levels of μOR BP_{ND} in chronic pain, including our initial migraine and allodynia data (DosSantos et al., 2012; DaSilva et al., 2014a; Nascimento et al., 2014a). Nonetheless, if the migraine mechanisms are not through a change in the μ-opioid system we need to explore alternative mechanisms in the future, such as the glutaminergic and GABA systems—data which will also be acquired during this study (see Aim3 alternative strategy)— hence, the results will still be interesting to report and investigate further. Second, μOR BP_{ND} levels at baseline will not be correlated with pain levels (also unlikely based on our data) (DaSilva et al., 2014a; DosSantos et al., 2014a). Although we are powered to perform all the analyses in this study, correlation analysis is a test that has low power. In the case of a statistical trend for a correlation, we will look at thalamus and other pain-related regions, and consider increasing the sample size by 20% and then describing these specific results as exploratory. We will also use different pain ratings (e.g., Pain Trek).

Does M1 HD-tDCS have modulatory effect on experimental and clinical measures in migraine?

Aim 2. To determine whether 10 daily sessions of M1 HD-tDCS have modulatory effect on clinical and experimental pain measures in migraine patients.

Our hypothesis is that 10 daily sessions of active M1 modulation, as compared to sham, will induce a greater analgesic after-effect in clinical and experimental pain measures. The focused targeting of M1 with HD-tDCS will lead to more precise sensory-discriminative modulation of pain (pain area and intensity). This will be evidenced in our

questionnaires (e.g., McGill, PANAS), pain tracking tools, and quantitative sensory tests.

Feasibility: (Aim 2.1) We preliminarily investigated the analgesic effects of M1-SO tDCS in chronic migraine (DaSilva et al., 2011c). Patients were randomized to receive 10sessions of active or sham M1-SO tDCS for 20 min with 2 mA, one session every other day ("second-daily"). The primary outcome measure was pain intensity. There was a significant interaction term (time vs. group) for the main outcome (pain intensity) and also for length of migraine episodes (ANOVA, p<0.05). Post-hoc analysis showed a significant improvement in the follow-up period for both outcomes in the active tDCS group only. In addition, patients in the active group showed a significant improvement in the clinician global impression. Nonetheless, it is now better understood that daily applications, instead of second-daily, leads to greater and faster increases in analgesia; hence, the selection of 10 daily sessions in our current protocol instead of every other day (Alonzo et al., 2012). Our findings reinforce the evidence that migraine measures have a positive response to M1-SO tDCS. However, our results also show that significantly spread electric fields are generated, not only in M1, but also in the thalamus and other pain-matrix regions (Figure 15), making it harder to dissect the direct role of M1 modulation on pain measures (DaSilva et al., 2011c).

Feasibility: (Aim2.2) In order to evaluate the analgesic effect of focally targeted M1 modulation, we have developed a novel M1 HD-tDCS montage with 2 x 2 electrode design, which we tested on a cohort of patients with another chronic trigeminal pain illness, temporomandibular disorder (TMD). Our computational model simulated our montage's current flow through tissues captured with 3D imaging, accounting for the tissue type, tissue shape, tissue resistance, electrode positioning, and strength of the current. Greatest density was focused on the lower region of the precentral gyrus/sulcus, targeting the putative homuncular craniofacial M1 region and immediately within the HD-tDCS 2 x 2 electrodes (Figure 16). This is the region where invasive motor cortex stimulation produces maximal analgesic effect for head and facial pain (Nguyen et al., 1999). We screened 78 patients for this study, and of those 24 (30.8%) were randomized, with 12 per group. All patients completed the active or placebo 5daily sessions of M1 HD-tDCS study according to the protocol. There were statistically significant between groups differences for sensorimotor measurements, including VAS 50% responders (p=0.04) at one-month follow-up (Table 2), pain free mouth opening at one-week follow-up (p<0.01), and most important: improvement of contralateral sensory-discriminative pain measures as collected by PainTrek (e.g., pain intensity, area and their summation), not ipsilateral pain measures, during the treatment week (p<0.01) (Table 3). In addition, we found "no" significant evidence that mood changes differed overall between the groups, as evaluated by the Positive and Negative Affect Scale (PANAS), indicating that our focused M1 HD-tDCS montage selectively modulated sensorimotor outcomes.

Potential pitfalls and alternative strategy: There is a possibility that at the end of the tDCS and PET study we get negative pain measures results. In this case, our 2nd

hypothesis was wrong, and only modulation of the pain-related neural networks will be seen in migraineurs (Aim3); however, this is unlikely based on previous successful experience with M1-tDCS and chronic migraine (DaSilva et al., 2011c), and experimental trigeminal pain (DosSantos et al., 2014b). A recent meta-analysis study in non-invasive M1 stimulation for chronic pain indicated an effective size of -0.86 (95% C.I., -1.54, -0.19) on the VAS (Zaghi et al., 2011). Another issue is the accuracy on targeting M1 in our montage. It is important to note that current can concentrate at distinct gyri/sulci sites so current flow, and thus brain activation, is not homogenous across an area of stimulation (Datta et al., 2009). Still, when external landmarks are used to target brain regions with HD-tDCS, computational models improve accuracy, but they are prediction models. In order to address this issue we will confirm the M1 location by using transcranial magnetic stimulation (Zaghi et al., 2010).

Feasibility: (Aim 3.1) We conducted analysis to demonstrate that tDCS can significantly modulate μ-opioid mechanisms and trigeminal pain measures in vivo, even immediately. This is a unique advance in pain translation research in humans, previously only possible in animal models. We examined with PET nine healthy volunteers with no history of chronic pain or systemic disorders. The protocol consisted of two PET scans, using [11C]carfentanil, a selective µOR radiotracer (Figure 17). The first PET provided a baseline evaluation of regional µOR BPND. During the second PET, placebo and active (2mA) M1-SO tDCS sessions were delivered sequentially, 20 min each, the same M1-SO tDCS montage as in our proposed migraine study. When analyzed separately, placebo and active tDCS were both associated with an acute reduction in µOR BPND, indicating activation of this neurotransmitter system in the PAG. In addition, the initial sham tDCS phase induced immediate activation of µORs in the left thalamus (Thal) and post-cingulate cortex, (PCC) and subsequently during the active tDCS phase in the left pre-frontal cortex (PreF) and precuneus (PreC). However, only after active tDCS was there significant improvement of pain thresholds measured by quantitative sensory testing, which were correlated with µOR system activation (DosSantos et al., 2014b). Our results suggest that immediate global analgesia induced by the M1-SO tDCS application, sham and active, can be related to the recruitment of endogenous muopioid mechanisms.

Analysis: (Aim3) First, we will examine changes in baseline μ OR BPND and in the activation of μ -opioid neurotransmission between pre- and post- 10 active daily HD-tDCS treatments. A mixed model of variance, accounting for age and other potentially influencing variables (e.g., plasma levels of estradiol, testosterone) will be employed. Increases in baseline μ OR BPND and in the activation of μ -opioid neurotransmission from pre- to post- 10 HD-tDCS sessions in migraine will be expected, with an approximation towards control values. The Spearman nonparametric test will then be used to assess the correlation between the percentage of change pre- and post- 10 M1-tDCS sessions in the thalamus and each region where it was observed, and that of the acute and chronic pain relief.

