migraine patients are associated with μOR BP_{ND} in the thalamus and other pain-related regions, even during interictal phase

(non-headache phase).

To determine whether 10 daily sessions of M1 HD-tDCS have modulatory effect on clinical and experimental pain measures in

migraine patients.

To investigate whether repetitive active M1 modulation induces/reverts thalamic µOR BP_{ND}, and whether those changes are associated with clinical and experimental pain

measures in migraine patients.

Population: 60 Patients age 18-65 years (inclusive) with episodic migraine

(ICHD-3-beta); AND

30 age and gender matched healthy subjects

Subjects will be recruited from the UMClinicalStudies.org database, the clinics at the University of Michigan (UM), and

from other clinics in the region

Phase: 2

Number of Sites: 1

Study Duration: 5 YRS

Investigation and Modulation of the Mu-Opioid Mechanisms in Migraine (In Vivo) Protocol HUM00107286 Version 0.6 12 December 2018

Subject Participation

Approximately 3 Months

Duration:

Description of Agent High-de

or Intervention:

High-definition transcranial direct current stimulation (HD-

tDCS)

Estimated Time to

4 Years

Complete Enrollment:

Schematic of Study Design I:

Screening Period	Week before daily M1 HD-tDCS sessions (Neuromodulation)	Active / Sham Neuromodulation (10 Daily Sessions) M-F x2		Week after daily M1 HD-tDCS sessions	Follow-up Period ⇒
First Appt	PET/MRI Sessions	5 Daily Sessions	5 Daily Sessions	PET/MRI Sessions	Follow-up at 1 Week and at 1 Month and 2 Months Following Neuromodulation

.....

Schematic of Study Design II:

Timing (Relative to Day 0)	Procedure		
PreScreening (Up to 8 weeks prior to Day 0)	Phone Call: IRB-Approved Prescreening Checklist/Script		
Screening (Up to 3 weeks prior to Day 0)	Informed Consent Demographics History and Physical Exam Questionnaires Randomization, once subjects have been consented		
PET and MRI #1 (Up to 1 week prior to Day 0)	QST PET #1 Workup Questionnaires (PET-specific) Pregnancy Test and Drug Screen CFN (11C-carfentanil) Injection MRI #1 Screening Form (MRI-specific) MRI Questionnaires*		
HD-tDCS x 10 Daily Sessions (Day 0 - 11; Week 1 and 2)	Migraine Active Questionnaires ≤2 mA current for 20 min/day x 10 days (M-F over 2 wks)	Migraine Sham Control Questionnaires ≤2 mA current for 30 sec at start plus 30 sec at end of session x 10 days (M-F over 2 wks)	* Healthy volunteers complete participation after PET/MRI#1 visit

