3. OBJECTIVES

3.1. STUDY OBJECTIVES

Objective #1:

To demonstrate that clinical and experimental pain measures in migraine patients are associated with µOR BPND in the thalamus and other pain-related regions, even during interictal phase (non-headache phase).

Objective #2:

To determine whether 10 daily sessions of M1 HD-tDCS have modulatory effect on clinical and experimental pain measures in migraine patients.

Objective #3:

To investigate whether repetitive active M1 modulation induces/reverts thalamic µOR BPND, and whether those changes are associated with clinical and experimental pain measures in migraine patients.

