3.4. SECONDARY OUTCOME MEASURES

Our hypothesis is that 10 daily sessions of active M1 HD-tDCS modulation will induce analgesic after-effect in clinical and experimental pain measures. The focused targeting of M1 with HD-tDCS will lead to precise sensory-discriminative modulation of pain (area and intensity). This will be evidenced in our questionnaires, tracking tools, and quantitative sensory tests.

We hypothesize that after 10 M1 HD-tDCS sessions there will be an increase in μ OR BP_{ND} (return toward healthy control values) in the thalamus and other pain-related brain areas in migraineurs at follow up, along with reductions in clinical/experimental pain measures.

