6. STUDY INTERVENTION

6.1. STUDY PROCEDURAL INTERVENTION(S) DESCRIPTION

We will conduct a single-center, sham-controlled, double-blinded study to prospectively investigate the neuromodulatory effects of M1 HD-tDCS in pain intensity and brain molecular neuroplasticity in a cohort of episodic migraine patients. The subjects will participate in 10 daily sessions (eg, Monday – Friday for two weeks), either active or sham M1 HD-tDCS.

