Two sets of analyses will be completed with the PET data: Volume of Interest Analysis: First, we will conduct a hypothesis-driven VOI analysis in which selected brain areas are examined. It offers the advantage of a relatively narrow search within the thalamus and other regions already known to be involved in the regulation of pain and in sex differences in these phenomena (e.g., anterior cingulate, insular cortex, nucleus accumbens, amygdala, periaqueductal gray for [11C]carfentanil scans). Predefined VOIs obtained from the data acquired in previous studies (Zubieta et al., 2001; Scott et al., 2008) will be utilized for this purpose and applied to the functional image data in stereotactic space. The VOIs will then be transferred to the μ -opioid receptor BP_{ND} Statistical Parametric Mapping: In subsequent analyses, statistical parametric maps will be obtained using whole brain image subtraction routines utilizing the images warped to stereotactic coordinates, as above. SPM analyses will be employed for the radiotracer, as shown in the Preliminary Data. Differences between conditions and subject groups will then be mapped into stereotactic space using t-maps of statistical significance and SPM8 and Matlab software, using a general linear model and correction for multiple comparisons (Friston et al., 1995). These maps are displayed superimposed over the anatomically standardized T1-weighted MRI of the subjects. This second analysis does not assume that specific regions are involved selectively, and a brain-wide search is performed on a voxel-by-voxel basis. Only gray matter pixels and regions with specific binding are included in the statistical parametric analyses (voxels with BP_{ND} values > 0.2) (Wager et al., 2007). For each subtraction analysis, one- or two-sample t-statistic values are calculated for each pixel using a pooled smoothed variance across voxels (Worsley et al., 1992). Areas of significant differences are detected using a statistical threshold that controls a Type-I error rate at p = 0.05 for multiple comparisons, which is estimated using the Euler characteristic (Worsley et al., 1992) based on the number of pixels in the gray matter and image smoothness (Friston et al., 1991). We will also use a multiple comparisons procedure that controls the false discovery rate (FDR; (Genovese et al., 2002), particularly in the case of preliminary analyses (years 2-3) that would not be fully powered for standard multiple comparisons

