11.2. SAMPLE SIZE CONSIDERATIONS

Taking into consideration a possible 20% dropout during the study, our sample size of 30 patients per group is a conservative number. For comparing two groups in Aim1 and Aim2, a sample size of 24 in each group will have 80% power to detect an effect size of 1.2 using a two-group t-test with a 0.05 two-sided significance level. For Aim3, baseline vs placebo/active M1 HD-tDCS, a sample size of 24 will have 80% power to detect an effect size of 0.8 using a paired t-test with a 0.05 two-sided significance level, allowing a wide range (0.1 to 1.0) of observable correlations within pairs.

Using the previous study, we approximated the SD as 20%/4 = 5% (range/4), and this gives us a detectable percentage change of 5*0.8=4 or higher.

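### Aim 3 is analysed and powered as change within an arm; no active-versus-sham contrast is specified or powered for mu-opioid binding

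*Combined protocol and SAP*

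**What the plan says.** The Aim 3 analysis paragraph in section 11.1 examines change in baseline BP_ND and in the activation of mu-opioid "neurotransmission between pre- and post- 10 active daily HD-tDCS treatments". It uses a mixed model adjusted for age and other influences, then correlates percentage change with pain relief. It names no sham comparator and no arm or arm-by-time term.

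Section 11.2 gives the power: "For Aim3, baseline vs placebo/active M1 HD-tDCS, a sample size of 24 will have 80% power to detect an effect size of 0.8", by a two-sided paired t-test at 0.05. The two-group calculation in the same section is for Aims 1 and 2 only.

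The objective and hypothesis are also worded without sham. Objective 3 in section 3.1 begins "To investigate whether repetitive active M1 modulation induces/reverts thalamic", and section 3.4 states "We hypothesize that after 10 M1 HD-tDCS sessions there will be an increase in" binding. For Aim 2, by contrast, section 11.1 says that "10 daily sessions of active M1 modulation, as compared to sham, will induce a greater analgesic after-effect".

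Some wording points the other way. Section 6.1 describes a sham-controlled study to "investigate the neuromodulatory effects of M1 HD-tDCS in pain intensity and brain molecular neuroplasticity". The opening of section 11 mentions active or sham sessions, ANOVA, and main effects of HD-tDCS on BP_ND. On the imaging maps it adds: "Differences between conditions and subject groups will then be mapped into stereotactic space". Section 11.6 leaves the final plan to a separate SAP, which is not in the text provided.

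**The concern.** A significant pre-to-post change in the active arm does not show that active stimulation caused it. Placebo response, a second scan and the passage of time act in both arms. Nor is a significant change in active alongside a non-significant one in sham a test of a difference between arms.

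Only the sham arm can separate these influences from HD-tDCS. The study schematic in the Protocol Summary says "Healthy volunteers complete participation after PET/MRI#1 visit", so the control group has no second scan.

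The protocol's own pilot (section 11.1, Aim 3.1 feasibility) reports that sham stimulation activated mu-opioid receptors, including in the left thalamus, which is the Aim 3 target. That effect was acute, came from nine healthy volunteers, and was a fall in BP_ND, whereas Aim 3 predicts a rise. It shows that sham cannot be presumed inert; it gives neither the size nor the direction of any bias here.

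At stake is the mechanistic conclusion of the randomised part of the trial. As written, it could rest on a within-arm test although both randomised arms are scanned twice.

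**Working it through.** **Inputs from section 11.2:** 24 evaluable patients per arm, effect size 0.8, two-sided 0.05, 80% power, within-pair correlation ρ of 0.1 to 1.0, SD 5%, 20% dropout. The particular values of ρ used below, and the sizes of any shared or sham change, are assumptions. Power is from the noncentral t distribution.

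**1. The plan's figure.** If 0.8 is in single-scan SD units, the paired effect is 0.8/√(2(1−ρ)). At ρ = 0.1 this is 0.8/√1.8 = 0.596, and power with n = 24 is 79.9%, so the stated 80% reproduces at the low end of the plan's correlation range. Dropout also reproduces: 24/(1−0.2) = 30. If 0.8 is instead in units of the SD of change, power is 96.3% and 15 patients would do. The plan does not say which SD is meant.

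**2. Rejection when HD-tDCS adds nothing.** Suppose both arms share the same shift, in SD of change. Let p be the power of the paired test at n = 24. With independent arms, the chance that active is significant and sham is not is p(1−p).

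| Shared shift (assumed) | Active-arm test significant, p | Active significant, sham not |
|---|---|---|
| 0.2 | 15.6% | 13.1% |
| 0.4 | 46.7% | 24.9% |
| 0.5 | 65.0% | 22.7% |
| 0.6 | 80.4% | 15.8% |

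A between-arm test is unaffected by a shared shift. In 8,000 simulated trials (ρ = 0.5, no arm effect), ANCOVA rejected in 5.0% to 5.2% at every shift.

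**3. Effect detectable with 80% power, 24 per arm.** The paired test detects 0.597 SD of change; a two-sample test detects 0.826 SD. (The 1.2 quoted for Aims 1 and 2 is not this limit: at 1.2, power is 98%.) In single-scan SD units:

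- paired: 0.597 × √(2(1−ρ))
- between-arm ANCOVA (approximate): 0.826 × √(1−ρ²)
- between-arm change score: 0.826 × √(2(1−ρ))

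| ρ | Paired | ANCOVA | Change score | ANCOVA relative to paired |
|---|---|---|---|---|
| 0.1 | 0.80 | 0.82 | 1.11 | 3% larger |
| 0.5 | 0.60 | 0.72 | 0.83 | 20% larger |
| 0.7 | 0.46 | 0.59 | 0.64 | 28% larger |

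If the plan's 5% is a single-scan SD, ANCOVA detects 4.1, 3.6 or 2.9 percentage points, against 4.0, 3.0 or 2.3 paired. If 5% is the SD of percentage change, an unadjusted comparison of change detects 0.826 × 5 = 4.1 points, against 0.597 × 5 = 3.0 paired.

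**4. Power for a between-arm difference of 0.8 single-scan SD (sham unchanged), 24 per arm.** At ρ = 0.1, 0.5 and 0.7: ANCOVA 78%, 88% and 97%; change score 52%, 77% and 94%.

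**5. If sham also changes.** Assume active changes by 0.8 SD and sham by 0.3 SD, a difference of 0.5. ANCOVA power is then 40%, 50% or 66% at the same three correlations.

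**The case against.** The strongest reply is that the protocol leaves room for the right test and that the text is incomplete. The opening of section 11 plans a global model that includes the main effect of HD-tDCS on BP_ND. The mixed model named for Aim 3 is described in the same words as the one used to compare patients with controls, so it need not be single-arm. The Aim 3 power statement mentions placebo as well as active, and section 11.3 says the more complex HD-tDCS models will be powered later. The Aim 3 heading does not appear in section 11.1 as extracted, and the SAP is unseen. Sections 3.1 and 3.4 name no sham for Aim 2 either, so their silence on Aim 3 shows little by itself.

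That last point is right, and the case should not lean on sections 3.1 and 3.4. The rest shows that a between-arm test is allowed; it does not show that one is chosen. The one paragraph that states the Aim 3 analysis is pre-to-post in active patients, and section 11.2 separates the paired Aim 3 calculation from the two-group one.

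Three further points are fair. The shared shifts are illustrative, and a change in the pilot's direction would oppose the predicted rise in baseline BP_ND. The planned sample roughly supports the between-arm test if sham does not change. The BP_ND effects of HD-tDCS are listed as secondary. These limit how serious the matter is; they do not make a within-arm test answer a between-arm question.

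**Conclusion.** The concern holds for the text provided. The stated Aim 3 analysis and its power both concern within-arm change, and no passage makes active versus sham the Aim 3 test or gives its power. Confidence is medium, because the separate SAP may specify the contrast.

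The false-credit rates in the table depend entirely on assumed shared shifts. The cost in detectable effect is firmer, being 3% to 28% over correlations of 0.1 to 0.7, but it assumes the plan's 24 evaluable patients per arm and an unchanged sham arm. If sham changes too, power for the real contrast falls well below 80%, and the current power statement does not show this.

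**What to change.** Make the main Aim 3 analysis an ANCOVA of post-treatment thalamic BP_ND on arm (active versus sham), adjusted for baseline BP_ND, age and sex, in all randomised patients with data. Age and sex match the covariates of the adaptive randomisation in section 5.4.1. Do the same for activation under the thermal pain challenge, adjusted for its pre-treatment value.

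A mixed model is a reasonable alternative. Baseline means should then be constrained to be equal across arms: an unconstrained arm-by-time term is valid, but it amounts to the change-score test and loses power at low correlation (52% against 78% for 0.8 SD at correlation 0.1). Report within-arm changes as descriptive.

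In section 11.2, restate the Aim 3 power for the between-arm difference, and say whether the 5% SD refers to a single scan or to percentage change. Align the SAP with this wording.

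The cost is text and a less favourable stated detectable effect, with lower power if sham patients also change. PET #1 and PET #2 are already scheduled in both randomised arms, so no extra scans are needed.
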